11. STATISTICAL ANALYSIS

11.1. Primary Analysis

Primary efficacy analysis:

CR-6283, Statistical Analysis Plan Version 2.0

Page 21 of 32

Visual Acuity

Distance monocular visual acuity (logMAR) will be tested under two conditions (bright illumination low contrast and dim illumination high contrast). Each condition will be analyzed separately using a Bayesian multivariate normal random-effects model to compare the Test and Control lenses. The regression model will include sequence of lens wear, lens type and first-order carryover effect as fixed effects. Clinical site and subject nested within clinical site will be included as random effects. Other subject characteristics such as gender and age will be included as fixed effects when appropriate.

The Model:

Let $y_{ijklm} = (y1_{ijklm}, y2_{ijklm}, y3_{ijklm})$ denote the visual acuity (logMAR) for the m^{th} subject at the l^{th} site, assigned to the i^{th} lens for the j^{th} eye using the k^{th} sequence at periods 1, 2, 3, respectively. The likelihood for y_{ijklm} is constructed as follows:

$$y_{ijklm} \sim N(\mu_{ijklm}, \Sigma)$$

Where $\mu_{ijklm} = (\mu1_{ijklm}, \mu2_{ijklm}, \mu3_{ijklm})^T$ and Σ is a 3X3 variance-covariance matrix. Here,

$$\begin{aligned}\mu1_{ijklm} &= \mu_0 + \pi_1 + \beta_1 \text{Lens}_{[i,k]} + \beta_2 \text{Sequence}_k + \gamma_l + \alpha_j \\ \mu2_{ijklm} &= \mu_0 + \pi_2 + \beta_1 \text{Lens}_{[i,k]} + \beta_2 \text{Sequence}_k + \beta_3 \text{Carry1}_{[i,k]} + \gamma_l + \alpha_j \\ \mu3_{ijklm} &= \mu_0 + \pi_3 + \beta_1 \text{Lens}_{[i,k]} + \beta_2 \text{Sequence}_k - \beta_3 \text{Carry1}_{[i,k]} + \gamma_l + \alpha_j\end{aligned}$$

In this model π_1, π_2, π_3 represent the effect of period with the constraint $\pi_1 + \pi_2 + \pi_3 = 0$. Lens will be determined by sequence k therefore lens i is denoted as a function of k. We define $\text{Lens}_i=0$ for the Control lens and $\text{Lens}_i=1$ for the Test lens, sequence is defined as: Sequence=0 for the order Control/Test/Test and Sequence=1 for order Test/Control/Control. The first-order carryover effect will be defined as carry=0 for the Control lens and carry=1 for the Test lens. So β_1 stands for the difference between the Test and Control lens with respect to visual performance. A negative β_1 indicates the Test performed better than the Control lens.

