$$\begin{aligned} \mu1_{ijkl} &= \mu_0 + \pi_1 + \beta_1 \text{Lens}_{[i,j]} + \beta_2 \text{baseline} + \beta_3 \text{Sequence}_j + \gamma_k \\ \mu2_{ijkl} &= \mu_0 + \pi_2 + \beta_1 \text{Lens}_{[i,j]} + \beta_2 \text{baseline} + \beta_3 \text{Sequence}_j + \beta_4 \text{Carry1}_{[i,j]} + \gamma_k \\ \mu3_{ijkl} &= \mu_0 + \pi_3 + \beta_1 \text{Lens}_{[i,j]} + \beta_2 \text{baseline} + \beta_3 \text{Sequence}_j - \beta_4 \text{Carry1}_{[i,j]} + \gamma_k \end{aligned}$$

In this model π_1, π_2, π_3 represent the effect of period with the constraint $\pi_1 + \pi_2 + \pi_3 = 0$. Lens will be determined by sequence j, therefore i is denoted as a function of j. We define Lens=0 for the Control lens and Lens = 1 for the Test lens, sequence is defined as: Sequence=0 for the order Control/Test/Test and Sequence=1 for order Test/Control/Control. The first-order carryover effect will be defined as carry=0 for the Control lens and carry=1 for the Test lens. So β_1 stands for the difference between the Test and Control lens with respect to CLUE comfort; A positive β_1 indicates the Test performed better than the Control.

We assume random site effects are independent and identically distributed (i.i.d) as $\gamma_k \sim N(0, \sigma_{site}^2)$ for site for $i=1, 2$ (lens), $j=1, 2$ (sequence), $k=1, 2, 3, 4, 5$ and 6 (site).

For the β coefficients, independent non-informative priors $N(0, 1000)$ will be used. For the variance of random effect of σ_{site}^2 an independent non-informative conjugate prior, inverse-gamma(0.001, 0.001) will be used. For Σ , non-informative conjugate priors inverse-wishart(3,S) will be used where S is a 3X3 variance-covariance matrix of y_{ijkl} . Starting values for the mean and variance of CLUE scores will be 60 and 400 (since standard deviation of CLUE is normalized to be 20), respectively. The Metropolis sampler algorithm as implemented in the SAS/STAT MCMC 14.2¹⁴ procedure will be used to estimate the posterior distribution of the unknown

parameters. Inferences will be made based on the 95% posterior credible intervals for relevant parameters.

Hypothesis Testing

The null and alternative hypotheses for CLUE comfort non-inferiority of the Test lens relative to the Control lens are as follows:

$$H_0: \beta_1 \leq -5$$

$$H_A: \beta_1 > -5$$

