Non-inferiority will be declared if the lower bound of the 2-sided 95% credible interval of the difference between the Test lens and the Control lens is greater than -5, i.e., $P(\beta_1 > -5) \geq 0.975$.

Vision Satisfaction in Bright Lighting

Vision satisfaction in bright lighting will be analyzed using a Bayesian multinomial model for ordinal data. The regression model will include sequence of lens wear, lens type, period and first order carryover effect. Clinical site and subject nested within clinical site will be included as random effects. Other subject characteristics such as age, gender, race and iris category will be included when appropriate.

The Model:

Let $y_{ijklm} = (y_{ijklm1}, y_{ijklm2}, y_{ijklm3}, y_{ijklm4}, y_{ijklm5})$ denote the rating for the m^{th} subject, from the l^{th} site, assigned to the i^{th} study lens in the j^{th} period using the k^{th} sequence. Possible values of y_{ijklm} are 1 if the subject rating of vision satisfaction in bright lighting are X and 0 otherwise (x=1 for Strongly Agree and X=5 for Strongly Disagree, respectively). The likelihood is constructed as follows:

$$y_{ijklm} \sim \text{Multinomial}(P_{ijklm1}, P_{ijklm2}, P_{ijklm3}, P_{ijklm4}, P_{ijklm5})$$

$$P_{ijklm1} = \gamma_{ijklm1}$$

$$P_{ijklmX} = \gamma_{ijklmX} - \gamma_{ijklm(X-1)} \quad 2 \leq n \leq 4$$

$$P_{ijklm5} = 1 - \sum_{x=1..4} P_{ijklmX}$$

$$\text{Logit}(\gamma_{ijklmX}) = \theta_n + \beta_1 \text{Lens}_{i[j,k]} + \beta_2 \text{Period}_{j1} + \beta_3 \text{Period}_{j2} + \beta_4 \text{Sequence}_k + \beta_5 \text{Carry}_{i[j,k]} + \gamma_l + \delta_{m(l)}$$

Where θ_n is the intercept for levels n=1,2,3,4, $P_{ijklm1} = \text{Pr}(\gamma_{ijklm1} = 1)$ with respect to the vision satisfaction in bright lighting item. We assume the random subject effects are independent identically distributed (i.i.d) as $\delta_{m(l)} \sim N(0, \sigma_{\text{subject}}^2)$ for subject m nested within clinical site l and

the random clinical site effects are i.i.d as $\gamma_l \sim N(0, \sigma_{site}^2)$ for $i=1,2$ (lens), $j=1, 2, 3$ (Period) $k=1, 2$ (Sequence) $l=1, \dots, 6$ (Site) $m=1, \dots, n_l$ (subject/site).

In this model, the lens I will be determined by the period j and sequence k , therefore i is denoted as a function of j and k . We define $Lens_i=0$ for the Control lens and $Lens_i=1$ for the Test lens. The cumulative odds ratio for having higher rating can be written as $OR=e^{\beta_1}$.

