Independent vague $N(0, 1000)$ priors for the regression coefficients β_i $i=1, \dots, 5$. For θ_n , we are considering the following priors

$$\begin{aligned}\pi_0(\theta_1) &\sim N(0, 100) \\ \pi_0(\theta_2 | \theta_1) &\sim N(0, 100) I(\theta > \theta_1) \\ \pi_0(\theta_3 | \theta_2) &\sim N(0, 100) I(\theta > \theta_2) \\ \pi_0(\theta_4 | \theta_3) &\sim N(0, 100) I(\theta > \theta_3)\end{aligned}$$

For the variance of random effects independent vague normal priors will also be used; $\sigma_p^2 \sim \text{inverse-gamma}(0.001, 0.001)$ and $\sigma_s^2 \sim \text{inverse-gamma}(0.001, 0.001)$. The Metropolis sample algorithm as implemented in the SAS/Stat MCMC Procedure will be used to estimate the posterior distributions of the unknown parameters. Inferences will be made based on the posterior credible interval for the relevant parameters.

Hypothesis Testing

The null and alternative hypotheses for superiority are as follows:

$$\begin{aligned}H_0 \quad OR &\leq 0.67 \\ H_A \quad OR &> 0.67\end{aligned}$$

Where OR represent the cumulative odds ratio of having higher rating of the Test lens compared to the Control lens. Non-inferiority will be declared if the lower bound of the 2-sided 95% credible confidence interval is above 0.67, i.e. $P(OR=e^{\beta_1} > 0.67 | y) = 0.975$.

Primary Safety Analysis:

Lens Fit Acceptance

Lens fit acceptance will be analyzed using a Bayesian Logistic regression random-effects model to estimate the proportion of subjects' eyes wearing the Test lens having acceptable lens fitting. The regression model will include period, sequence of lens wear and first order carryover effect as fixed effects. Site and subject will be included in the model as random effects.

Let $y_{ijklm}=1$ if an acceptable lens fit is observed for eyes wearing the Test lens only and $y_{ijklm}=0$ otherwise for the m^{th} subject, from the l^{th} site, for the i^{th} eye in the j^{th} period using the k^{th} sequence.

$$y_{ijklm} \sim \text{Binary} (p_{ijklm})$$

$$p_{ijklm} = \frac{\exp(\mu_{ijklm})}{1 + \exp(\mu_{ijklm})}$$

$$\mu_{ijklm} = \beta_0 + \beta_1 \text{Lens}_{i[j,k]} + \beta_3 \text{period}_{j1} + \beta_4 \text{period}_{j2} + \beta_5 \text{sequence}_k + \beta_6 \text{Carry1}_{i[j,k]} + \gamma_1 + \delta_{m(l)} + \alpha_{j(m(l))}$$

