We assume the random subject eye effects are i.i.d as $\alpha_{j(m(l))} \sim N(0, \sigma_{eye}^2)$ for eye nested within subject within clinical site, the random effect for subject are i.i.d as $\delta_{m(l)} \sim N(0, \sigma_{subject}^2)$ for subject nested within clinical site and the random clinical site effects are i.i.d as $\gamma_m \sim N(0, \sigma_{site}^2)$ for i=1, 2 (eye) , j=1, 2, 3 (period) k=1, 2 (Sequence) l=1, ...6 (Site) m=1, ...n_l(subject/site).

For the β coefficients, independent non-informative priors $N(0, 10000)$ will be used. For the variance of random effects of $\sigma_{eye}^2, \sigma_{subject}^2$ and σ_{site}^2 , independent non-informative conjugate priors inverse-gamma (0.001, 0.001) will be used. The Metropolis-Hastings algorithm as implemented in the SAS/STAT 14.2 PROC MCMC procedure will be used to estimate posterior distributions of the unknown parameters. Inferences will be made based on the posterior credible interval for the relevant parameters.

Hypothesis Testing

With respect to acceptable lens fit the null and alternative hypothesis for superiority is as follows:

$$\begin{aligned} H_0 &= p \leq 0.90 \\ H_1 &= p > 0.90 \end{aligned}$$

Where, p represents the proportion of subject eyes that achieve acceptable fit for the Test lens.

Where p is calculated as:

$$p = \frac{\exp(\mu)}{1 + \exp(\mu)}$$

$$\text{And } \mu = \beta_0 + \beta_1 + \frac{\beta_3}{3} + \frac{\beta_4}{3} + \frac{\beta_5}{2} + \frac{\beta_6}{2}$$

Success for acceptable fit will be declared if the lower bound of the 2-sided 95% credible interval of the proportion is greater than 0.90; i.e. $P(p > 0.90) \geq .975$.

If the full planned model fails to converge, reduced versions may be considered.

Primary safety analysis:

Slit Lamp Findings

Grade 3 or higher slit lamp findings will be analyzed using a Bayesian Logistic regression random-effects model to compare the Test and Control lenses. The regression model will include baseline slit lamp findings, lens type, period, sequence of lens wear and first order carryover effect. Site and subject will be included in the model as random effects.

Let $y_{ijklmn}=1$ if a Grade 3 or higher SLF is observed and $y_{ijklmn}=0$ otherwise for the n^{th} subject, from the m^{th} site, assigned to the i^{th} study lens for the j^{th} eye in the k^{th} period using the l^{th} sequence.

$$y_{ijklmn} \sim \text{Binary}(p_{ijklmn})$$

$$p_{ijklmn} = \frac{\exp(\mu_{ijklmn})}{1 + \exp(\mu_{ijklmn})}$$

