$$\mu_{ijklmn} = \beta_0 + \beta_1 Lens_{ij[k,l]} + \beta_2 \text{Baseline SLF}_1 + \beta_3 period_{k1} + \beta_4 period_{k2} + \beta_5 \text{sequence}_k + \beta_6 Carry1_{i[k,l]} + \gamma_m + \delta_{n_{(m)}} + \alpha_{j_{(n(m))}}$$

We assume the random subject eye effects are i.i.d as $\alpha_{j_{(n(m))}} \sim N(0, \sigma_{eye/subject/site}^2)$ for eye nested within subject within clinical site, the random effect for subject are i.i.d as $\delta_{n_{(m)}} \sim N(0, \sigma_{subject/site}^2)$ for subject nested within clinical site and the random clinical site effects are i.i.d as $\gamma_m \sim N(0, \sigma_{site}^2)$ for $i=1,2$ (lens), $j=1, 2$ (eye) , $k=1, 2, 3$ (period) $l=1, 2$ (Sequence) $m=1, \dots, 6$ (Site) $m=1, \dots, n_m$ (subject/site).

In this model, the lens I will be determined by the period k and sequence l, therefore i is denoted as a function of j and k. We define $Lens_i=0$ for the Control lens and $Lens_i=1$ for the Test lens. The odds ratio for having a lower rate of SLFs can be written as $OR=e^{\beta_1}$.

For the β coefficients, independent non-informative priors $N(0, 10000)$ will be used. For the variance of random effects of $\sigma_{eye}^2, \sigma_{subject}^2$ and σ_{site}^2 , independent non-informative conjugate priors inverse-gamma (0.001, 0.001) will be used. The Metropolis-Hastings algorithm as implemented in the SAS/STAT 14.2 PROC MCMC procedure will be used to estimate posterior distributions of the unknown parameters. Inferences will be made based on the posterior credible interval for the relevant parameters.

Hypothesis Testing

The null and alternative hypothesis for Non-inferiority is as follows:

$$H_o: OR \geq 2$$

$$H_A: OR < 2$$

Where OR represents the cumulative odds of the Test lens having a lower rate of Grade 3 SLFs compared to the Control lens and is calculated as $OR=e^{\beta_1}$. Non-inferiority will be established if the upper limit of the 2-sided 95% credible interval is below 2, i.e. $P(OR < 2 | y)=0.975$.

If the full planned model fails to converge, reduced versions may be considered. In the event that the number of Grade 3 or higher SLFs is too small Grade 2 or higher SLFs will be analyzed and tested as described above.

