11.2. Secondary Analysis

Secondary efficacy analysis:

CLUE Overall Quality of Vision and Handling

CLUE Overall Quality of Vision and Handling will be analyzed and test in the exact same manner as CLUE Overall Comfort.

Overall Quality of Vision Indoors

Overall quality of vision indoors will be analyzed and tested in the same manner as vision satisfaction in bright lighting. The only difference between the two models are the response set used to assess each item. For this model,

Let $y_{ijklm} = (y_{ijklm1}, y_{ijklm2}, y_{ijklm3}, y_{ijklm4}, y_{ijklm5})$ denote the rating for the m^{th} subject, from the l^{th} site, assigned to the i^{th} study lens in the j^{th} period using the k^{th} sequence. Possible values of y_{ijklm} are 1 if the subject rating of overall quality of vision indoors are X and 0 otherwise (x=1 for Excellent and X=5 for Poor, respectively).

Secondary safety analysis:

Not Applicable

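### SAP 11.1 gives Carry1 no values by sequence and period in the logMAR and CLUE models; coded as the preceding lens, its plus-then-minus signs leave beta1 unidentified

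*SAP*

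**What the plan says.** SAP 11.1 models logMAR acuity and CLUE comfort with one mean equation per period. Carry1 is absent in period 1. In period 2 it has a plus sign: "Sequence}_k + \beta_3 \text{Carry1}_{[i,k]} + \gamma_l + \alpha_j" for logMAR and "Sequence}_j + \beta_4 \text{Carry1}_{[i,j]} + \gamma_k" for CLUE. In period 3 both equations print it with a minus sign. The only definition, given for both models, is "The first-order carryover effect will be defined as carry=0 for the Control lens and carry=1 for the Test lens". No table gives its value for each sequence and period. The index list for the logMAR model shows carry1 as 1, 2, which does not match the 0/1 coding.

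The same model serves two secondary endpoints (SAP 11.2): "CLUE Overall Quality of Vision and Handling will be analyzed and test in the exact same manner as CLUE Overall Comfort".

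The other SAP 11.1 models index carryover by period and sequence and give it a single plus sign: "\beta_4 \text{Sequence}_k + \beta_5 \text{Carry}_{i[j,k]} + \gamma_l + \delta_{m(l" for vision satisfaction, "\beta_6 \text{Carry1}_{i[j,k]} + \gamma_1 + \delta_{m(l" for lens fit and "\beta_6 Carry1_{i[k,l]} + \gamma_m" for slit lamp findings.

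**The concern.** Protocol 4.2 chose the 2x3 design because earlier 2x2 crossover studies of the Test lens showed carryover, and because this design can estimate it within subjects. The printed equations should deliver that without guesswork. Under the ordinary meaning of first-order carryover they do not: the change of lens between periods 2 and 3 is counted once in the coding and again in the sign, and the two cancel.

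Two primary endpoints are affected (logMAR under both lighting conditions, and CLUE comfort), plus CLUE vision and handling. SAP 5.1 requires every primary hypothesis to be met, so one model that cannot conclude blocks the primary objective. The fallback, "If the full planned model fails to converge, reduced versions may be considered", is stated for lens fit and slit lamp findings only.

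**Working it through.** The plan states no figure to reproduce here; the question is whether beta1 can be estimated.

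**Inputs.** From SAP 11.1: sequences T/C/C (Sequence = 1) and C/T/T (Sequence = 0); Lens = 1 for Test; period effects summing to zero; N(0, 1000) priors on the betas. I read 1000 as a variance, because the SAP writes its random effects as N(0, sigma²). From SAP 8.4: the covariance matrices and 105 completers, taken as 52.5 per sequence.

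**Step 1: identification with the printed signs.** Let d1, d2, d3 be the T/C/C mean minus the C/T/T mean in each period, S the sequence coefficient and c the carryover coefficient. Period effects cancel, and d1 = beta1 + S under every coding.

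| Carry1 is | T/C/C, periods 2 and 3 | C/T/T, periods 2 and 3 | d2 | d3 | Rank (of 6) |
|---|---|---|---|---|---|
| Preceding lens | 1, 0 | 0, 1 | -beta1 + S + c | -beta1 + S + c | 5 |
| Period-1 lens | 1, 1 | 0, 0 | -beta1 + S + c | -beta1 + S - c | 6 |
| Current lens | 0, 0 | 1, 1 | -beta1 + S - c | -beta1 + S + c | 6 |

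In the first row d2 and d3 are the same equation, which leaves two equations for three unknowns. Moving (beta1, S, c) by (+t, -t, +2t) changes none of the differences, and the period effects absorb the rest. Coding Carry1 as 1/2 also gives rank 5.

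**Step 2: a single plus sign, as in the vision satisfaction and slit lamp models.** The preceding lens now gives d2 = -beta1 + S + c and d3 = -beta1 + S - c, so rank 6. The period-1 lens gives -beta1 + S + c twice, and the current lens gives -beta1 + S - c twice, so both have rank 5. None of these three codings identifies beta1 under both sign patterns.

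**Step 3: size under the preceding-lens coding with the printed signs.** The data leave t free, so the prior sets it. With variance 1000 on beta1, S and c and flat period terms, Var(t) = 1000/(1 + 1 + 4) = 166.7, and SD = 12.91.
- logMAR: half-width 1.96 × 12.91 = 25.3. At no difference, P(beta1 < 0.05) = Φ(0.05/12.91) = 0.50.
- CLUE comfort at a true +5, with the SAP 8.4 covariance: posterior mean 4.15, SD 13.03. The interval is 4.15 ± 25.5, or -21.4 to +29.7. P(beta1 > -5) = Φ(9.15/13.03) = 0.76.

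**Step 4: size under an identified coding.** Each rank-6 combination above gives beta1 = [d1 - (d2 + d3)/2]/2.
- CLUE: the variance of the within-subject contrast (1, -1/2, -1/2) is 397.18 + (411.89 + 370.83)/4 - 142.48 - 144.55 + 210.90/2 = 411.3. Then Var(beta1) = (1/4)(2/52.5)(411.3) = 3.92, SD 1.98, half-width 3.9. With posterior mean 4.98 at a true +5, the interval is +1.1 to +8.9.
- logMAR: the contrast variance is 1.5 × (0.003518 - 0.000374) = 0.004716. With one value per subject, Var(beta1) = (1/4)(2/52.5)(0.004716) = 0.0000449, half-width 0.013. With both eyes treated as independent (105 units per sequence), the half-width is 0.009.

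**The case against.** The strongest defence is that the printed signs make sense as they stand. In both sequences the preceding lens switches between periods 2 and 3. If Carry1 is fixed for a sequence at the period-1 lens, plus then minus expresses exactly that switch, and the model is equivalent to ordinary first-order carryover. The subscripts carry no period index, which fits this, and Lens keeps one sign throughout while Carry1 does not. This stands: a working reading exists and needs no change to the equations.

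It does not settle the matter. Lens has the same period-free subscripts and must vary by period. The SAP uses the name first-order carryover, whose usual meaning is the preceding lens. That is also the only one of the three codings that identifies beta1 in the vision satisfaction and slit lamp models. The SAP does not define carryover values there either. Its note that the lens is determined by period and sequence could be read as the current lens, but that coding has rank 5 with a single plus sign.

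The equations in Protocol 14.5 put a minus on Sequence in period 2, and with that sign the preceding-lens coding has rank 6. They do not help, because SAP section 1 says that the SAP supersedes the protocol's statistical section.

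A reader might also infer that the coding would be chosen after seeing the data and so could move the result. The documents do not support this: every identified coding in Step 4 gives the same beta1, and SAP section 1 requires deviations to be reported.

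**Conclusion.** The concern holds conditionally. The SAP leaves Carry1 undefined by sequence and period in the logMAR and CLUE models. Under the standard meaning its signs make beta1 unidentified, and non-inferiority could not be declared at the planned effects. A reader might infer that the printed model is unidentified outright, or that it could produce a false claim. Neither follows: with the period-1 lens the same equations identify beta1, and the failing case gives an interval so wide that it could not pass unnoticed.

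The rank results are exact. Site and eye random effects and the CLUE baseline covariate do not restore identification. The interval widths hold the SAP 8.4 covariances fixed and omit those terms. If the same prior is also put on the two free period terms, the logMAR half-width is 21.9 or 23.4 and the CLUE probability 0.80 or 0.78, depending on which two are free, so the conclusion is unchanged. The only historical acuity summary shown is for high illumination and high contrast, which is neither endpoint condition. With its Test-lens SD of 0.0825 (SAP Table 7) and the same correlation, the identified logMAR half-width would be 0.013 to 0.018, still well inside the margin of 0.05.

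**What to change.** Before database lock, add to SAP 11.1 a table of Carry1 by sequence and period, with signs that match, for the logMAR and CLUE models. Either of these works:

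- **(a) Preceding lens.** T/C/C is 1 in period 2 and 0 in period 3; C/T/T is 0 in period 2 and 1 in period 3; plus sign in both periods. This agrees with the single-sign models elsewhere in the SAP.
- **(b) Period-1 lens.** T/C/C is 1 and C/T/T is 0 in both periods, with the present plus and minus signs.

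Both give the same beta1 estimator. Do not change the sign without fixing the coding: the period-1 lens with plus in both periods is itself rank 5. Correct the 1, 2 index for carry1 at the same time, and check that the program codes the variable as tabulated.

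The cost is a four-value table, plus one sign in each of two equations under (a) and no equation change under (b). Data collection and sample size are unaffected.

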Acceptable lens fit will be assessed for each subject eye at all scheduled study visits (fitting [visit 1] and follow-up [visit 2]). Fit acceptance rate will be based on the lens fit acceptance of eyes wearing the Test lens only. Fit rates of the Control lens will also be collected but are not a primary endpoint.

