5. STATISTICAL HYPOTHESES FOR STUDY OBJECTIVES

5.1. Primary Hypotheses

All primary hypotheses must be met in order to satisfy the primary objective of this study.

1. The Test lens will be non-inferior to the Control lens with respect to Distance Monocular logMAR Visual Acuity at the two-week follow-up evaluation under both lighting conditions (Bright illumination low contrast and dim illumination high contrast). A non-inferiority margin of 0.05 logMAR will be used.

2. The Test lens will be non-inferior to the Control lens with respect to the percentage of eyes with Grade 3 or higher Slit Lamp Findings (Biomicroscopy) across all follow-up visits (scheduled and unscheduled). A non-inferiority odds ratio margin of 2 will be used.
3. The proportion of eyes with acceptable fit will be greater than 90% across all visits (scheduled and unscheduled) for all subjects wearing the Test lens.
4. The Test lens will be non-inferior to the Control lens with respect to CLUE Overall Comfort at the two-week follow-up evaluation. A non-inferiority margin of -5 points will be used.
5. The Test lens will be non-inferior to the Control lens with respect to Vision satisfaction in bright lighting at the two-week follow-up evaluation. A non-inferiority cumulative odds ratio margin of 0.67 will be used.

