visual performance was analyzed using a linear mixed model. Lens type was included as the only fixed effect. A compound symmetric (CS) covariance matrix was used to model the correlation between measurements on the same subject across study periods. Below is the variance-covariance matrix used in the visual performance model.

$$\sum_{\text{visual performance}} \begin{pmatrix} 0.003518 & 0.000374 & 0.000374 \\ 0.000374 & 0.003518 & 0.000374 \\ 0.000374 & 0.000374 & 0.003518 \end{pmatrix}$$

Acceptable Lens Fit

Acceptable lens fit is a binary response as $y=1$ if a subject eye has an acceptable fit and $y=0$ otherwise. Indicated by the historical data there was only 1 observed unacceptable lens fittings for the Test lens therefore, the common reference rate of 95% was selected for the sample size calculation, since this is considered to be a more conservative reference proportion. Assuming a correlation 0.80 between measurements within the same subject and period (intra-eye correlation); and assuming a correlation of 0.50 between measurements within the same subject across periods. A total of 2000 replicating trials were simulated to estimate a sample size with a minimum statistical power of 80%.

Slit Lamp Findings

There were no Grade 3 or higher SLFs observed in any of the historical studies. Assuming no difference between study lenses and a correlation 0.80 between left and right eyes within the same subject and period; and a correlation of 0.50 between measurements within the same subject across periods (intra-subject correlation). A reference rate of no more than 5% was assumed (worse-case scenario) with a non-inferiority odds ratio margin of 2. A total of 2000 replicating trials were simulated, each replicated sample was analyzed using a generalized estimating equation (GEE) model with a binary distribution and the logit as the link function. Each model included lens type as the only fixed, eye was included as a random effect. The Odds ratio and corresponding 95% confidence interval was used estimate differences between the Test and Control lenses. The upper limit of each 95% confidence interval was compared to 2; if the upper limit was below 2 then NI=1; otherwise NI=0. Statistical power was calculated at the average NI. A sample size of 50 was chosen to achieve a minimum statistical power of 80%.

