The non-inferiority odds ratio margin of 2 corresponds to no more than a 5% difference between the Test and Control lenses assuming the Control reference rate does not exceed 5%.

Individual Questionnaire Items

Overall quality of vision outdoors and vision satisfaction in bright lighting sample size estimates were calculated using historical data from [REDACTED]. One-thousand boot strap samples were simulated based on the historical data. For each replicated sample a generalized linear mixed model was used with a multinomial distribution and the cumulative logit as the link function. Lens wear sequence, lens type, period and first order carryover effect were included in the model as fixed effects. A variance component (VC) covariance structure was used to model the measurements between subjects across study periods.

The non-inferiority cumulative odds ratio margin of 0.67 corresponds to no more than a 10% difference between the Test and Control lenses assuming there is no difference between study lenses.

Table 11: Sample Size Estimates and Power Calculations for Primary Endpoints

Endpoint	Number per Subjects to Complete	Power
Distance Monocular Visual Acuity (logMAR)	4	80%
SLFs (Grade 3 or Higher)	50	80%
Acceptable lens Fit	65	80%
CLUE Comfort	30	87%
Vision Satisfaction in Bright Lighting	48	81%

Table 12: Sample Size Estimates and Power Calculations for Secondary Endpoints

Endpoint	Number per Subjects to Complete	Power
CLUE Handling	30	81%
CLUE Overall Quality of Vision	30	82%
Overall Quality of Vision Indoors	95	81%

As indicated in Table 11 and 12 above, the sample size chosen for this study was primarily driven by overall quality of vision indoors. The plan is to enroll 120 eligible subjects with a target of 105 subjects to complete the study. During the enrollment period, the subject drop-out rate will be closely monitored, if an unexpectedly high dropout rate is observed, then the targeted total enrollment number may be increased accordingly to ensure that a minimum of 105 subjects complete the study.

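### The lens-fit model cannot be estimated from the Test-only eyes the SAP specifies, and its p is taken at zero random effects, so the rule does not test the proportion in H0

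*SAP*

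**What the plan says.** SAP 11.1 (Lens Fit Acceptance) tests H0: p ≤ 0.90 and declares success if P(p > 0.90) ≥ 0.975. It states: "Where, p represents the proportion of subject eyes that achieve acceptable fit for the Test lens". It then sets p = exp(μ)/(1 + exp(μ)) with μ = β0 + β1 + β3/3 + β4/3 + β5/2 + β6/2. The coefficients belong to the intercept, Lens, two period terms, sequence and carryover. The model equation also has site, subject and eye random effects, but none of them enters μ.

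The response is coded 1 "if an acceptable lens fit is observed for eyes wearing the Test lens only". SAP 4.1 agrees: "Fit acceptance rate will be based on the lens fit acceptance of eyes wearing the Test lens only". Protocol 2.2 says the same. On the fixed effects the SAP says: "The regression model will include period, sequence of lens wear and first order carryover effect as fixed effects". Lens type is not in that list, yet the printed equation contains β1·Lens.

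SAP 5.1 states the hypothesis as "The proportion of eyes with acceptable fit will be greater than 90" per cent, and every primary hypothesis must be met. In SAP 8.4, "the common reference rate of 95% was selected for the sample size calculation", and the Table 11 row "Acceptable lens Fit" gives 65 subjects and 80% power. Protocol 14.5 has the same equation and hypotheses but no formula for p; the SAP supersedes it.

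**The concern.** Two things do not fit together.

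- **Data and equation.** With Test eyes only, Lens is constant, and the Test lens is worn in just three sequence-by-period cells. The formula for μ may then not be determined by the data.
- **p and H0.** An inverse-logit at zero random effects is the probability for an eye at a typical site and subject. It is not the proportion of eyes. Above 0.5 it always exceeds that proportion when the random-effect variance is positive.

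These belong to two alternative readings and do not act together. In reading A (Test-only data, equation as written) a good lens can fail. In reading B (model made estimable) a lens at or below 0.90 can pass. Which one applies would depend on a programming choice the SAP does not settle, for a hypothesis on which the primary objective depends.

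**Working it through.** **The plan's own figure.** I could not reproduce 65 subjects and 80% power. With the correlations in SAP 8.4 (0.80 within period, 0.50 across periods), a 95% rate and Test-only eyes, 65 subjects give about 0.30 (logit scale) or 0.55 (identity scale) two-sided. SAP 8.4 does not state the analysis model for that simulation, so this is noted only as background.

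**Reading A: estimability.** Sequences are TCC and CTT (SAP 3.1). Sequence is coded 1 for TCC. Carryover is 1 after Test and 0 otherwise, as defined for the other SAP models.

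| | Intercept | Lens | Period 1 | Period 2 | Sequence | Carry |
|---|---|---|---|---|---|---|
| TCC, period 1 | 1 | 1 | 1 | 0 | 1 | 0 |
| CTT, period 2 | 1 | 1 | 0 | 1 | 0 | 0 |
| CTT, period 3 | 1 | 1 | 0 | 0 | 0 | 1 |
| SAP μ | 1 | 1 | 1/3 | 1/3 | 1/2 | 1/2 |

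The three cells have rank 3; adding the μ row gives rank 4. By hand, TCC period 1 would need weight 1/3 (period column) and also 1/2 (sequence column). The weights would have to sum to 1, but 1/3 + 1/3 + 1/2 = 7/6 and 1/2 + 1/3 + 1/2 = 4/3.

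The closest weights are 0.375, 0.250 and 0.417. They leave a residual of squared length 0.0347, on which only the prior acts. Reading N(0, 10000) as a variance, the prior-only SD of μ is 100 × √0.0347 = 18.6 logits, however large the trial.

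With unlimited data at a true 0.95, the mean of μ is 1.0417 × 2.944 = 3.07. Then P(p > 0.90) = Φ((3.07 − 2.20)/18.63) = 0.519. At 0.99 it is 0.555. Reaching 0.975 needs a mean μ of 2.20 + 1.96 × 18.63 = 38.7.

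**Reading A: simulation.** All runs use 105 subjects (53 TCC, 52 CTT), hence 53 × 2 + 52 × 4 = 314 Test eye-periods, equal rates for both lenses and the SAP's variance priors. No random-effect variance is in the documents, so the logit-scale SDs are assumed. Pass rates with a subject effect fitted, 80 trials per setting:

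| True rate | SAP rule, SD 0.5/1/2 | Averaged p |
|---|---|---|
| 0.90 | 0/0/0% | – |
| 0.95 | 0/0/0% | 93/84/66% |
| 0.98 | 8/5/13% | 99–100% |
| 0.99 | 33/35/36% | 99–100% |

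Three failures in 314, one per Test cell (311/314 = 99.0% acceptable), give P(p > 0.90) = 0.57, or 0.64 with a subject effect; averaged p gives at least 0.999. Zero failures give 0.999, and one failure 0.983–0.994. Those last two pass because a cell without failures drives μ upwards towards the scale of the prior.

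**Reading B: both lenses fitted.** Six cells give rank 6, and μ becomes estimable. Its weights on the cell logits are:

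- Test: 0.417 (TCC period 1), 0.208 (CTT period 2), 0.375 (CTT period 3)
- Control: +0.125 (TCC period 2), −0.042 (TCC period 3), −0.083 (CTT period 1)

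A Control cell with no failures has a logit governed by the prior, so it can move the Test p.

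**Reading B: p at zero random effects.** Averaging the inverse-logit over a normal random effect, a p of 0.90 by the SAP formula is a population proportion of 0.891, 0.866, 0.797 and 0.715 at SD 0.5, 1, 2 and 3.44. SD 3.44 matches the planning correlation of 0.50 on the binary scale at a 0.90 rate; on the latent scale that correlation gives √(π²/3) = 1.8.

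False passes at a true 0.90 (ranges span repeated simulations):

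| Model | SAP p, SD 0.5/1/2/3.44 | Averaged p |
|---|---|---|
| Test-only intercept, subject effect | 5–9/13–21/69–81/about 99% or more | 1–5% |
| Same, with subject, eye and site effects | 8/26/55%/not run | 1–2% |
| Both lenses, Lens effect only | 2–5/20–23/92–93/100% | 2–5% |
| Both lenses, all six fixed effects | 9/34/98%/not run | 2–3% |

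The six-effect rule is also erratic for good lenses. At a true 0.99 it passes in 68–82% of trials (60 per setting), against 100% with averaged p.

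**The case against.** The algebra is not in dispute; its reach is.

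- **Expected rates are far above 0.95.** SAP Table 8 shows one unacceptable Test fit and protocol Table 7 shows none. The 95% rate was chosen as conservative. With zero or one failure the rule passes under both readings. This stands, and it limits the practical effect. At a true 0.9985 (1 in 680 eyes, a denominator taken from the slit-lamp table), 93–94% of reading A trials have failures in at most one Test cell, the pattern that passes. SAP Table 8 prints 0.05%, which would make trouble rarer still. But these lenses come from a new production line evaluated clinically for the first time here.
- **Reading A may not be intended.** The Lens term and the shape of μ suggest a model with both lenses. That is plausible, but it contradicts the stated data, and the zero-random-effect problem remains.
- **The SAP allows reduced models.** The clause applies only on non-convergence, names no model and leaves the formula for p unchanged.
- **The variances are assumed.** True. The direction is certain for any positive variance; the size is not. At SD 0.5 false passes are only 2–9%.
- **Coding.** The visual acuity and CLUE models put a minus sign on period-3 carryover. The fit equation has none. With the minus sign, the both-lens design falls to rank 5 and μ is not estimable even then.
- **One result per eye-period** was simulated, although fit is assessed at fitting and at follow-up. This is a simplification.

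**Conclusion.** The concern holds. On the stated Test-only data, μ is not identified by the likelihood and the prior largely decides the outcome: 0 of 240 trials passed at the 95% planning rate. Once μ is made estimable, the rule tests a probability at zero random effects, which is too lenient near 0.90. Excess false passes are small at SD 0.5, clear at SD 1 and gross at SD 2 or more.

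The rank result rests only on the design and the printed formula. The 18.6 logits also rest on reading the second prior parameter as a variance. The false-pass rates rest on the assumed SDs and on 105 completers. This should be fixed, but with zero or one unacceptable Test fit the decision would probably be the same.

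**What to change.** 1. Reconcile the Test-only wording with the Lens term: state that eyes wearing either lens enter the model and that p is taken for the Test cells only.
2. Replace the 1/3 and 1/2 contrast. In each MCMC draw, average the inverse-logit over the fitted site, subject and eye distributions and over the three Test sequence-period cells, weighted by Test eye-periods. Apply P(p > 0.90) ≥ 0.975 to that p.
3. Re-simulate the 80% in Table 11 with the final model.

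Subjects leave the study after an unacceptable fit (for example Protocol 7.2, Visit 2, step 2.9). With that built in, the both-lens averaged rule had false-pass rates of 1–5% (six effects) or 2–7% (Lens effect only). If the sponsor keeps Test-only data, Lens and the other non-estimable terms should go and the same averaging be used. The SAP should then disclose that false passes were 2/6/19/25% at SD 0.5/1/2/3.44 when subjects leave. For that reason the both-lens version is preferable.

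The cost is SAP wording and a few lines of post-processing, with no new data. Power is lower at some variances: 93/83/67% at a true 0.95 and SD 0.5/1/2 in the six-effect both-lens model, where the SAP's p passed in 95–98%.
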